9.1 STUDY DESIGN

This is a non-interventional study with existing data. It will be a retrospective, observational, non-interventional, new user design, real world study of Commercial Insurance and Medicare beneficiaries, using administrative claims data for the period of 15th September 2016 through 31st March 2020.

Patients initiating Stiolto, or Trelegy will be identified using pharmacy claims database). The date of the first prescription claim (on or after 15th September 2017) will be defined as the index date. Patients will be required to have a diagnosis of COPD (ICD-9-CM: 491.xx, 492.xx, 496.xx; ICD-10-CM: J41-J44) on two separate medical claims. Patients 40 years or older will be included in the study. Patients will be required to have continuous enrolment for 12 months prior to the index date. Patients will be excluded if they show any

Proprietary confidential information © 2022 Boehringer Ingelheim International GmbH or one or more of its affiliated companies

use of COPD maintenance medications (ICS, LABA or LAMA in any combination), during the baseline period of six months pre-index date. This will satisfy the criteria for being considered as treatment naive. Patients with two separate medical claims with a diagnosis of asthma, lung cancer, interstitial lung disease, or cystic fibrosis during the study period will be excluded. Using propensity score matching (PSM) technique, we will develop matched cohorts of patients between Stiolto initiators and Trelegy initiators. We will conduct 1:1 matching using nearest neighbour matching approach with a caliper of 0.2. Exacerbation will be defined as a COPD hospitalization (severe exacerbation) or Emergency Department (ED) visit (severe exacerbation) with COPD, or use of approved respiratory antibiotics (e.g., Azithromycin) \pm Oral CorticoSteroids (OCS) medications within \pm 7 days of the office/outpatient visit (moderate exacerbation) as the primary diagnosis. Multiple exacerbations occurring within 14 days of each other will be considered as a single exacerbation and will be per the higher severity. A schematic of the study design is presented below in Figure 1.

Boehringer Ingelheim Non-Interventional Study (NIS) Protocol BI Study Number 1237-0121

c38026921-01

Proprietary confidential information © 2022 Boehringer Ingelheim International GmbH or one or more of its affiliated companies

Figure 1 Study Design

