Patients will be followed the index date to record time to first incidence of exacerbations, record time to first incident case of pneumonia, and HCRU. The analysis will be, "on treatment", analysis. Patients will be followed from the index date until the earliest of the first occurrence of outcome event, switch in index treatment (Stiolto or Trelegy), discontinuation of index treatment (Stiolto or Trelegy), the end of the study period, the end of continuous health plan eligibility, or (for main analyses) one year after index date. Hazard ratios and their 95% CI from proportional hazards models will be used to assess differences in the risk of COPD exacerbation and pneumonia.

Proprietary confidential information © 2022 Boehringer Ingelheim International GmbH or one or more of its affiliated companies

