Inclusion Criteria:

- \geq 40 years of age as of the year of the index date
- At least one pharmacy claim for Stiolto Respimat or Trelegy Ellipta between 15 September 2017 and 31st March 2020.
 - For Stiolto Respimat users, the first pharmacy claim of FDC of Tiotropium + Olodaterol (5/5 mcg) will be defined as the index date.
 - For Trelegy Ellipta users, the first pharmacy claim of FDC of Fluticasone Furoate + Umeclidinium + Vilanterol (100/62.5/25 mcg), will be defined as the index date.
- Two medical claims (at least one claim on index date or before in the baseline period) with an ICD-9/10 diagnosis code(s) for COPD in any position during the study period (baseline ± post index date).
- At least one year of continuous medical and pharmacy health plan eligibility prior to the index date is required (to allow a baseline period for the covariates and characterizing the study population).

Exclusion Criteria:

- To increase the likelihood of a true diagnosis of COPD, we will exclude all patients with two medical claims of asthma, cystic fibrosis, lung cancer, or interstitial lung disease in any position on separate dates of service during the study period.
- To restrict the cohort to first line maintenance therapy of Stiolto Respimat or first line maintenance therapy of Trelegy Ellipta we will exclude; patients on LAMA. monotherapy; LABA monotherapy; ICS monotherapy; free or FDC of ICS+LABA, LAMA+LABA, ICS+LABA+LAMA therapy within six months prior to index date.
- Pharmacy claims for multiple index medications on the index date.
- Pharmacy claims for non-index COPD maintenance medications on the index date.

Proprietary confidential information © 2022 Boehringer Ingelheim International GmbH or one or more of its affiliated companies

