9.3 VARIABLES

The definitions for exacerbations are as below.

- A severe exacerbation will be defined as follows:
 - An inpatient admission or an ER visit with a COPD diagnosis code in the primary position; or
 - An inpatient admission or an ER visit with a diagnosis code for acute respiratory failure in the primary position and a COPD diagnosis code in any position; or
 - An inpatient admission or an ER visit with a diagnosis code for acute respiratory failure in the primary position + an inpatient admission or an ER visit within ±7 days with a COPD diagnosis code in any position.
- A moderate exacerbation will be defined as follows:
 - An ambulatory (office or outpatient) visits with a COPD diagnosis code in any position + a pharmacy claim for an oral corticosteroid (OCS) prescription within ±7 days of the office/outpatient visit; or

Proprietary confidential information © 2022 Boehringer Ingelheim International GmbH or one or more of its affiliated companies

- \circ An office or outpatient visit with a COPD diagnosis code in any position + a pharmacy claim for respiratory antibiotic prescription within ±7 days of the office/outpatient visit; or
- An office or outpatient visit with a COPD diagnosis code in any position + a pharmacy claim for an OCS + a pharmacy claim for respiratory antibiotic prescription within ±7 days of the office/outpatient visit.
- Pneumonia diagnosis: Binary indicators will be created to identify patients with a diagnosis of 1) pneumonia (Appendix 1). The time to first pneumonia diagnosis, and time to first pneumonia, during follow-up will also be captured.
- Pneumonia-related hospitalization: Binary indicators will be created to identify
 patients with an acute hospitalization with diagnosis of 1) pneumonia in any
 position (Appendix 1) The time to first pneumonia-related hospitalization during
 follow-up will also be captured.
- COPD exacerbation and/or pneumonia diagnosis: Binary indicators will be created to identify patients with each of the following composite outcomes: severe COPD exacerbation or an acute hospitalization with a diagnosis of pneumonia in any position, severe COPD exacerbation or a hospitalization with a diagnosis of pneumonia in any position, any COPD exacerbation or pneumonia diagnosis in any position, and any COPD exacerbation or pneumonia diagnosis in any position. Time to event variables will be created for each composite outcome during the follow-up period.

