9.3.2 Outcomes

9.3.2.1 Primary Outcomes

The primary outcome event for effectiveness is time to first COPD exacerbation after cohort entry. The event is defined as follows:

- Severe exacerbation:
 - Hospitalization with a principal discharge diagnosis of COPD and/or
 - An emergency department (ED) visit with a discharge diagnosis of COPD
 - An inpatient admission or an ER visit with a diagnosis code for acute respiratory failure in the primary position and a COPD diagnosis code in any position
- Moderate exacerbation:
 - \circ An antibiotic for a respiratory condition dispensed \pm an OCS

Time to the first COPD exacerbation will be measured from index date until the occurrence of a hospitalization for COPD (severe exacerbation) or ED visit for COPD (severe exacerbation) or prescription of an antibiotic \pm an OCS on the same day (moderate exacerbation). Severe and moderate exacerbations were considered as a composite for main analyses. Sensitivity analyses will include stratification by exacerbation severity.

Exacerbations will be categorized as moderate or severe and a count of any (severe or moderate), severe, and moderate will be provided.

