9.3.3 Covariates

Patient characteristics at baseline will be assessed for Stiolto and Trelegy users overall and stratified by history of exacerbation.

The covariates included in the Propensity Score Matching (PSM) will include all the below covariates including the ones defined during the 12-month pre-index baseline period and chronic comorbid conditions.

- Gender
- Age group (years, categorical and a continuous variable)
- Calendar year of cohort entry
- Region
- Insurance type (e.g., Commercial, Medicare)
- Season of index date (winter, spring, summer, fall)

Additional characteristics that will be defined during the 12-month pre-index baseline period:

- Previous acute COPD exacerbation (measured both overall and in the 30 days prior to cohort entry), categorized as 0, 1, or ≥2.
 - All exacerbations (Moderate+Severe)
 - Hospitalizations (Severe)
- Use of other respiratory drugs in the 12-month pre-index period:
 - Short-acting beta-agonists
 - Short-acting Anticholinergics
 - Methylxanthines
 - o LAMA
 - o LABA

Proprietary confidential information © 2022 Boehringer Ingelheim International GmbH or one or more of its affiliated companies

- o ICS
- o ICS/LABA
- Use of antibiotics commonly prescribed for a respiratory condition (e.g., azithromycin)
- Use of OCS
- Oxygen Use
- Pulmonary Rehabilitation

Chronic comorbidities were defined using diagnoses identified during all available data prior to the index date, and included

- Quan-Charlson Comorbidity Index score/individual comorbidities
- Cardiovascular disease
- Diabetes
- Renal failure
- GERD
- Arthritis
- Osteoporosis
- Cancer (excluding basal cell carcinoma)
- Baseline pneumonia diagnosis
- Baseline acute bronchitis diagnosis
- Diagnosis of dyspnea during baseline identified using ICD 9 786.0x and ICD 10 R06.0x
- Diagnosis of obesity during baseline identified using ICD 9 278.xx and ICD 10 E66.xx
- Diagnosis of alcohol dependence during baseline identified using ICD 9 303.xx, 305.0x and ICD 10 F10.xx
- Smoking dependence during baseline identified using ICD 9 305.1 and ICD 10 F17.xx
- Tobacco use or cessation counselling*

*We anticipate limited capture of lifestyle variables known to be risk factors and potential confounders, including obesity, smoking status, and excessive alcohol consumption.

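### Claims dated after the index date help decide who enters the cohort, so the primary hazard ratio carries a selection risk whose size and direction the documents do not give

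*Combined protocol and SAP*

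**What the plan says.** Section 9.1 sets the data window, "using administrative claims data for the period of 15th September 2016 through 31st March 2020", and starts follow-up at index: "Patients will be followed from the index date until the earliest of the first occurrence of outcome event". Section 9.3.1 counts outcomes from the day after index to day 365.

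Two eligibility rules in section 9.2.2 look past index.

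- **Exclusion.** Two claims for "asthma, cystic fibrosis, lung cancer, or interstitial lung disease in any position on separate dates of service during the study period" remove the patient. Section 9.1 and the abstract repeat the rule. The stated purpose is a truer COPD diagnosis.
- **Inclusion.** Two COPD claims are needed. Only one must fall on or before index; the other may show "COPD in any position during the study period (baseline ± post index date", so it may come later.

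Elsewhere the protocol limits windows to pre-index time when it means to. The treatment-naïve rule covers the six months before index, and section 9.3.3 states: "Chronic comorbidities were defined using diagnoses identified during all available data prior to the index date". The study-period wording is therefore not naturally read as baseline only.

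The planned sensitivity analyses concern a 30-day gap and all available follow-up (9.3.1), exacerbation severity (9.3.2.1) and selected covariates (9.7). None changes the eligibility window. Section 9.7.1 promises a description of cohort formation but no split of removals by timing. Section 9.9 does not mention the issue.

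**The concern.** Eligibility in a new-user cohort should be settled by the time follow-up begins. Here it is not.

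Under section 9.3 every exacerbation involves a COPD-coded visit; the moderate definition, for example, begins "An ambulatory (office or outpatient) visits with a COPD diagnosis code in any position". A patient with one COPD claim by index who exacerbates qualifies through the outcome. The same patient, event-free and with no later COPD claim, is dropped. Section 9.3.2.1 defines the moderate event differently ("An antibiotic for a respiratory condition dispensed", with or without an oral corticosteroid) and asks for no COPD code. Under that version the mechanism works mainly through severe events.

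The exclusion can remove a patient, together with an event already observed, because of diagnoses coded during or after follow-up. If either kind of selection is related to the outcome and differs between Stiolto and Trelegy initiators, the primary Cox hazard ratio is shifted.

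**Working it through.** The plan gives no figure for this selection, so there is none to reproduce. The calendar windows come from the documents. Every input to the ratios below is assumed.

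**1. Windows.** 15 September 2017 to 31 March 2020 is 928 days. For the earliest index date the exclusion window runs 928 − 365 = 563 days beyond the 12-month cap. With index dates spread uniformly and everyone enrolled to the end (both assumed), the mean excess is 563²/(2 × 928) = 171 days; disenrolment would shorten it.

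**2. Second-claim rule.** Let r be the one-year event risk (25-40%), s the share with exactly one COPD claim by index, q the chance that such a patient gets a later COPD claim apart from the event (60-80%), and p the share of events carrying a COPD code (1 under section 9.3; 25-40% assumed under section 9.3.2.1). There is no true treatment effect.

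Kept with an event: 1 − s(1−p)(1−q). Kept without: 1 − s(1−q). Observed risk = r × kept with event / (r × kept with event + (1−r) × kept without).

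Example, r = 0.25, q = 0.6, p = 1:
- s = 0.25: 0.25/(0.25 + 0.75 × 0.90) = 0.2703
- s = 0.20: 0.25/(0.25 + 0.75 × 0.92) = 0.2660
- ratio 1.016

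**3. Exclusion rule.** With e and n the shares removed among patients with and without an event, observed risk = r(1−e)/[r(1−e) + (1−r)(1−n)].

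Example, r = 0.25:
- e = 5%, n = 2%: 0.2375/0.9725 = 0.2442
- e = 7%, n = 2.5%: 0.2325/0.96375 = 0.2412
- ratio 1.012

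**4. Results** (ratio of observed risks; invert if the arms are swapped).

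| Scenario | Modest arm difference | Large arm difference |
|---|---|---|
| Second claim, p = 1 | 1.006-1.016 (s 25% vs 20%) | 1.012-1.067 (s 30-35% vs 15-20%) |
| Second claim, p = 0.25-0.40 | 1.002-1.007 | 1.003-1.028 |
| Exclusion | 1.010-1.012 (5%, 2% vs 7%, 2.5%) | 1.011-1.080 (5%, 1.5-2% vs 10-15%, 3-5%) |
| Same selection in both arms | 1.00 | 1.00 |

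An on-treatment Cox simulation (true HR 1; 2,000,000 per arm; assumed discontinuation hazard 0.9 per year) gave slightly larger values. Modest: 1.009-1.020 (second claim, p = 1) and 1.015 (exclusion). Large: up to 1.083 and 1.093. Equal selection: 1.003-1.004, Monte Carlo standard error 0.002-0.003. The two rules were worked separately; together they could add or offset.

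**5. How plausible are the large values?** The standardized difference of two shares a and b is |a − b|/√{[a(1−a) + b(1−b)]/2}. For one-claim shares, 20% vs 25% gives 0.05/0.417 = 0.12; 15-20% vs 30-35% gives 0.23-0.47. The plan treats anything above 0.10 as imbalance. As a yardstick only, since removal is not a baseline variable, the exclusion shares among patients with events give 0.08 (5% vs 7%) and 0.19-0.34 (5% vs 10-15%).

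**The case against.** **Matching deals with it.** Section 9.3.3 matches on, among others, "Previous acute COPD exacerbation (measured both overall and in the 30 days prior to cohort entry", respiratory drugs, calendar year and season. Section 9.7.1 adds data-derived variables to the score and puts any variable still imbalanced into the outcome model. Baseline COPD-related utilization, close to a claim count, is measured in section 9.3. This stands in part: such variables may narrow arm differences in one-claim patients and in window length. But claim count is not a listed covariate, and baseline matching cannot undo conditioning on later claims.

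**Section 9.9 promises bias analysis as appropriate.** It does, but without specification and chiefly for unmeasured confounding. Neither eligibility rule is named.

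**The assumed inputs drive the size.** True. If 90% of event-free one-claim patients get a later COPD claim, the second-claim ratios fall to 1.003-1.004 (modest) and 1.006-1.015 (large). Section 9.2.2 also requires separate service dates for the exclusion diagnoses but not for the COPD claims, so two claims from one visit may qualify and the one-claim group may be small.

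**It is small beside sampling error.** With 6036 matched patients and 25-40% risk there are about 1509-2414 events. The 95% interval factor exp(1.96 × 2/√events) is about 1.11 to 1.08, so 1-2% is a minor part of it. That also stands, although this error does not shrink with sample size, and the overall hazard ratio that section 9.5 cites from the literature is only 0.97.

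**The remedy trades one bias for another.** Patients whose asthma is coded only after index would stay in. Section 7 names asthma-COPD overlap among the reasons to use triple therapy, so they could be commoner in the Trelegy arm. This is a fair caution. It is why the whole-period rule should remain as a sensitivity analysis, and why the choice between one and two pre-index COPD claims is a matter of judgement.

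**Stronger readings to resist.** A reader might infer that the hazard ratio is biased towards one product. The documents do not say how post-index coding differs by arm, and swapping the assumed arms inverts every ratio. A reader might also point to retention through the criteria: 3996/15,538 = 25.7% for Stiolto against 5121/35,686 = 14.4% for Trelegy. That is all criteria combined, and no part of the gap can be assigned to post-index claims.

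**Conclusion.** The structural point is certain from the text: claims after index can both remove and admit patients, and an exacerbation can be the admitting claim. The effect on the primary hazard ratio is not established. It is about nil if selection is alike in both arms and can go either way if it differs. Under the assumed inputs it is about 0-2% for modest arm differences. The 7-9% at the top of the calculated range requires one-claim shares, or removals among patients with events, that differ far more than the plan's own 0.10 limit would tolerate. A reader might take 9% as the expected error; nothing in the documents supports that. The point should be fixed before the comparative analysis because the remedy is cheap and nothing planned would reveal the problem.

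**What to change.** In sections 9.1 and 9.2.2 and the abstract:

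1. Assess the four exclusion diagnoses on claims on or before the index date, using the 12-month baseline that every patient has. Use all available pre-index data as a sensitivity analysis; that look-back varies from 365 to 1293 days with index date, so it suits the secondary role better.
2. Let no post-index COPD claim decide entry. Prespecify both a one-claim and a two-claim pre-index definition, one as primary and one as sensitivity analysis. Choose before outcomes are seen and after re-running the section 9.5 count against the 2000-pair minimum in section 9.7.
3. Keep the current whole-period rule as a prespecified sensitivity analysis.

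In section 9.7.1, add an attrition table by criterion, arm and timing (pre- or post-index), including patients admitted only by a post-index COPD claim. State the issue in section 9.9.

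**Cost.** Wording changes, a re-run of the cohort query and one table. With the one-claim definition eligibility only widens, so eligible counts cannot fall below 3996 and 5121, taking those as counted under the present criteria. The two-claim definition removes patients now admitted by a later claim, so its net effect on numbers is unknown. The matched 3018 may move either way because the scores are refitted; it could fall by (3018 − 2000)/3018 = 33.7% before missing the minimum. Some diagnostic specificity is lost, possibly unequally by arm; the whole-period sensitivity analysis shows how much that matters.

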9.2.2 Study Population

Patients initiating Stiolto, or Trelegy will be identified using pharmacy claims (database). The date of the first prescription claim (on or after 15th September 2017) will be defined as the index date. Patients will be required to have a diagnosis of COPD (ICD-9-CM: 491.xx, 492.xx, 496.xx; ICD-10-CM: J41-J44) on two separate medical claims. Patients 40 years or older will be included in the study. Patients will be required to have continuous enrolment for 12 months prior to the index date. Patients will be excluded if they show any use of COPD maintenance medications (ICS, LABA or LAMA in any combination), during the baseline period of six months pre-index date. This will satisfy the criteria for being considered as treatment naive. Patients with two separate medical claims with a diagnosis of asthma, lung cancer, interstitial lung disease, or cystic fibrosis during the study period will be excluded. Using propensity score matching (PSM) technique, we will develop matched cohorts of patients between Stiolto initiators and Trelegy initiators. We will conduct 1:1 matching using nearest neighbour matching approach with a caliper of 0.2. Exacerbation will be defined as a COPD hospitalization (severe exacerbation) or Emergency Department (ED) visit (severe exacerbation) with COPD, or use of approved respiratory antibiotics (e.g., Azithromycin) \pm Oral CorticoSteroids (OCS) medications within ± 7 days of the

Proprietary confidential information © 2022 Boehringer Ingelheim International GmbH or one or more of its affiliated companies

office/outpatient visit (moderate exacerbation) as the primary diagnosis. Multiple exacerbations occurring within 14 days of each other will be considered as a single exacerbation and will be per the higher severity.

Patients will be followed after the index date to record time to first incidence of exacerbations, record time to first incident case of pneumonia, and HCRU. The analysis will be, "on treatment", analysis. Patients will be followed from the index date until the earliest of the first occurrence of outcome event, switch in index treatment (Stiolto or Trelegy), discontinuation of index treatment (Stiolto or Trelegy), the end of the study period, the end of continuous health plan eligibility, or (for main analyses) one year after index date. Hazard ratios and their 95% CI from proportional hazards models will be used to assess differences in the risk of COPD exacerbation and pneumonia.

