9.7 DATA ANALYSIS

Summary measures will include standard descriptive statistics (e.g., mean, standard deviation, median and range for continuous variables; counts and percentages for categorical variables). However, for any baseline characteristics with significant differences (Standardized differences (SD) greater than 0.10 (10%)) after PSM matching, these characteristics will be included as covariates in the regression models, or we will develop interaction terms to match on or discontinue the study if major channeling (SD>10%) is observed. Basically, a two-step approach: The first step will be to characterize the patients after PS matching to see whether balance can be achieved (based on SD) and at least 2000 patients from the Stiolto cohort can be matched with at least 2000 patients in the Trelegy cohort before proceeding to the second step of doing the comparative analysis. Sensitivity analyses may be performed on a select set of covariates considered to be prognostic factors. In the event of study discontinuation, partial results (all analysis leading up to and including PSM) will be provided in a final report.

A Cox proportional hazards models will be used on the time to first COPD exacerbation with treatment as a covariate. Comparisons will be made between treatment cohorts using HR and will be presented with associated 95% CI. To account for variable lengths of follow-up observation time, population annualized results will be provided (annualized costs [e.g., Sum of total costs/Sum of total follow-up patient years for each cohort]). The annualized cost may be modelled as dependent variable in a Generalized Linear Model with treatment cohort as a covariate and the follow-up patient years as an offset for each cohort.

Comparisons will be made between treatment cohorts and will be presented with associated 95% CI. Additionally, descriptive techniques that account for the length of observation time measure will be used appropriately. Per patient per month calculations will not be performed because of bias concerns. Appropriate tests comparing the Stiolto cohort and the Trelegy cohort (e.g., standardized differences, McNamara's tests, paired t-tests, sign tests) will be used based on the distribution of the measure. Patients not matched will be excluded from the post-match analysis.

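### A six-month washout defines maintenance-naive although 12 months of pharmacy data are required, so the plan permits users from months 7-12 and, on one reading of the index rule, returning Stiolto users

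*Combined protocol and SAP*

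**What the plan says.** - **Washout.** The exclusion criteria in Section 9.2.2 remove patients with single-agent or combined LAMA, LABA or ICS treatment, ending with "ICS+LABA+LAMA therapy within six months prior to index date". The narrative of the same section places the test "during the baseline period of six months pre-index date" and adds: "This will satisfy the criteria for being considered as treatment naive". Section 9.1 and the abstract give the same six months.
- **Look-back.** The inclusion criteria state: "At least one year of continuous medical and pharmacy health plan eligibility prior to the index date is required". Section 9.3.1 defines the baseline as day -364 through the index date, whereas the narrative of Section 9.2.2 calls six months the baseline period.
- **Covariates.** Section 9.3.3 puts "Use of other respiratory drugs in the 12-month pre-index period" into the propensity score and lists LAMA, LABA, ICS and ICS/LABA among the drugs. Neither this list nor the baseline medication classes in Section 9.3 name LAMA/LABA combinations, the class to which Appendix 2 assigns Stiolto.
- **Index date.** Section 9.1, repeated in the narrative of Section 9.2.2, states: "The date of the first prescription claim (on or after 15th September 2017) will be defined as the index date". The criteria list says instead: "For Stiolto Respimat users, the first pharmacy claim of FDC of Tiotropium + Olodaterol (5/5 mcg) will be defined as the index date". That sub-item gives no date, but it sits under a criterion requiring a claim between 15 September 2017 and 31 March 2020.
- **Dates.** Section 7 puts Stiolto's approval in May 2015 and Trelegy's in September 2017. Section 9.1 starts the claims data on 15 September 2016.
- **Longer washout.** None is planned, not even as a sensitivity analysis.

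**The concern.** The title, the goal and every comparative exacerbation and pneumonia objective concern maintenance-naive patients or new treatment initiation, and Section 9.1 calls the study a new-user design. A patient who used a maintenance inhaler eight months before index, lapsed and then started Stiolto or Trelegy is neither naive nor on first-line treatment, yet passes every criterion. Patients who return to treatment are selected by what happened the first time: how they tolerated it, why they stopped, and why they needed it again. If the two arms hold different shares of such patients, the hazard ratio mixes that history with the drug contrast. If the shares are equal, the estimate still describes a population other than the one named in the objectives.

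**Working it through.** **1. The unscreened window.** The baseline runs from day -364 to day 0, which is 365 days. Taking six months as about 183 days, 365 - 183 = 182 days, or 182/365 = 50%, are never tested for maintenance drugs. At the earliest index date (15 September 2017) the data already reach back 365 days, to 15 September 2016. A 12-month test therefore needs no data beyond what eligibility already requires.

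**2. What the covariate list implies.** Under a six-month exclusion, a 12-month indicator for LAMA, LABA, ICS or ICS/LABA can be positive only through use in months 7-12. Listing these drugs as matching variables makes sense only if such patients can be present.

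**3. Return to the same drug, by arm.**
- *Stiolto, Section 9.1 rule.* Someone with Stiolto claims in January 2017 and none again until October 2017 takes the October claim as index, the earliest on or after 15 September 2017, and has nothing in the last six months. This patient qualifies as an initiator.
- *Stiolto, criteria-list rule.* If the index is read as the earliest pharmacy claim in the data, the same patient's index date falls in January 2017, outside the window, and the patient does not qualify. The two wordings give opposite answers.
- *Trelegy.* With approval in September 2017 there is essentially no use before the window, so the earliest pharmacy claim in the window is the earliest of all.
- *Reach of a 12-month test.* The last pre-window day is 14 September 2017, and adding 364 days gives 13 September 2018. For index dates after that, a pre-window Stiolto claim lies outside the 12-month baseline. Only a search of all available data would find it.

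**4. The plan's own power figure.** Section 9.5 and the abstract tie at least 80% power to about 3,000 patients per cohort, with no alpha, target hazard ratio or event rate. The figure cannot be reproduced. At 3,018 per arm and two-sided 0.05 (assumed from the 95% CI), the cited 9.0% versus 16.1% for severe exacerbation gives over 99.9% power. The cited hazard ratio of 0.97 gives at most 22%, even if every patient had an event.

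**5. Cost of a 12-month washout.** The share f with use in months 7-12 is not in the documents, so the values below are assumptions. Matched n = 3,018 × (1 - f). By Schoenfeld's formula, the hazard ratio detectable at 80% power is exp[-2(1.960 + 0.842)/√d], where d = 2 × n × 0.30 events (30% with an event, also an assumption).

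| f | n per arm | Detectable HR |
|---|---|---|
| 0% | 3,018 | 0.877 |
| 5% | 2,867 | 0.874 |
| 10% | 2,716 | 0.870 |
| 20% | 2,414 | 0.863 |
| 30% | 2,113 | 0.854 |
| 33.7% | 2,000 | 0.851 |

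The last row is the limit set by Section 9.7, which requires that "at least 2000 patients from the Stiolto cohort can be matched": (3,018 - 2,000)/3,018 = 33.7%. If 20% or 40% have an event, going from 3,018 to 2,000 per arm moves the detectable hazard ratio from 0.851 to 0.820, or from 0.892 to 0.869.

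**The case against.** The six-month rule is stated consistently and is the plan's declared definition of naive. The 12-month eligibility is given another purpose, namely covariates and description, and no text promises patients who were never treated. Washout length is a trade-off between purity and sample. All of that stands, and it is why a change to the main cohort rule is optional here.

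Matching also helps. Twelve-month LAMA, LABA, ICS and ICS/LABA use enters the propensity score, Section 9.7.1 allows data-derived variables, and residual standardized differences above 10% go into the outcome model or may stop the study. This partly balances earlier treatment between arms. It does not make those patients naive. Because LAMA/LABA combinations are not named, it need not balance earlier Stiolto use.

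A reader might infer that recently treated patients do enter, that they collect in the Stiolto arm, and that the comparison is therefore biased. The documents do not support this. Anyone treated in the last six months is excluded. Use of other maintenance drugs in months 7-12 is open to both arms, and a Trelegy initiator may have used Stiolto then. The asymmetry concerns only return to the same drug, and it rests on the Section 9.1 wording prevailing over the criteria list.

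Nor does the 34% margin show that the loss is free. The 2,000 is a floor for proceeding, and the power statement is tied to about 3,000. Exclusions made before matching need not carry through to the matched count one for one.

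**Conclusion.** The point holds as a gap between label and rule: as written, the plan permits patients with maintenance use in months 7-12 to enter a cohort that its objectives call naive and first-line. The index-date wordings conflict on whether a lapsed Stiolto user may enter as an initiator. Neither the number of such patients nor the direction of any bias can be derived from the documents. At an assumed 5-20% of the 3,018 matched per arm, about 151 to 604 patients per arm would be affected. Removing them would leave 2,867 to 2,414 and move the detectable hazard ratio from 0.877 to between 0.874 and 0.863 (80% power, two-sided 0.05, 30% with an event, proportional loss through re-matching). This does not invalidate the design, but it should be addressed before the comparative analysis, because the remedy uses data already held.

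**What to change.** 1. Reconcile Sections 9.1 and 9.2.2. Define the index claim as the earliest pharmacy claim for the index drug in all available data from 15 September 2016, and exclude patients whose earliest pharmacy claim for that drug precedes 15 September 2017.
2. Pre-specify an analysis of the primary endpoint that excludes maintenance use over the full 12-month baseline, with the propensity score re-estimated and the cohorts re-matched. Drop the LAMA, LABA, ICS and ICS/LABA use covariates there, since they become empty. If feasibility counts allow, make this the main rule.
3. Where the six-month rule is kept, add LAMA/LABA and triple combinations to the covariate and baseline class lists, and report how many patients in each arm had maintenance use in months 7-12.
4. Use one length for the term baseline period.

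The cost is programming, a new feasibility count, and some sample and precision. The at-least-80% power statement must be restated for the smaller cohort, with alpha, hazard ratio and event rate given. Stiolto use before 15 September 2016, or before a patient's own enrolment, stays unobservable and belongs among the limitations in Section 9.9.
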